TITLE: A Prospective Trial of Neural Progenitor Cell Sparing Radiation Therapy Plus Temozolomide for Newly Diagnosed Glioblastoma Multiforme

Research Site:	The Johns Hopkins University School of Medicine
Principal Investigator:	[name]., M.P.H. Department of Radiation Oncology [name] [contact] [contact] Email: [contact]
Co-Investigators:	[name]., Department of Radiation Oncology [name]., Department of Medical Oncology [name]., Department of Neuropsychology [name], N.P., Department of Oncology [name]., Department of Oncology [name]., Ph.D., Department of Oncology [name]., Department of Neurosurgery [name]., Department of Neurology [name]., Department of Psychiatry

Statistician:

[name]., M.S. [contact] Email: [contact]

Study Coordinators:

[name] [contact] [contact]

Research Nurses:

[name], R.N., B.S.N. [contact] [contact] [name] [contact] [contact]

[name], R.N.,

[contact]

[contact]

[contact] [contact]

> [name], R.N. [contact] [contact]

[name], B.S.

SCHEMA

Patient Eligibility: (See Section 3)

Newly diagnosed, histologically confirmed glioblastoma multiforme. Radiation and medical oncologist recommends adjuvant radiation plus temozolomide. Must begin therapy within 12 weeks of biopsy or surgery. No prior brain radiation. Age \geq 18 years. KPS > 60%. Signed informed consent.

Treatment Plan: (See Section 5)

Required sample size: 30 patients Anticipated accrual: 4-5 patients per month

TABLE OF CONTENTS

SC	HEM	P	age ii
ыc		•	11
1.	OBJE	CTIVES	1
	1.1	Primary Objectives	1
	1.2	Secondary Objectives	1
2.	BACH	KGROUND	1
	2.1	Study Disease and Rationale	1
	2.2	Temozolomide	3
	2.3	Correlative Studies Background	3
3.	PATI	ENT SELECTION	5
	3.1	Eligibility Criteria	5
	3.2	Exclusion Criteria	6
	3.3	Inclusion of Women and Minorities	6
4.	REGI	STRATION PROCEDURES	6
5.	TREA	ATMENT PLAN	7
	5.1	Surgery and Chemotherapy	7
	5.2	Radiation	7
	5.3	Duration of Follow Up	9
	5.4	Criteria for Removal from Study	9
6.	STUE	DY CALENDAR	10
7.	MAN	AGEMENT OF TOXICITY	11
	7.1	Acute Toxicity	11
	7.2	Late Toxicity	13
8.	STAT	ISTICAL CONSIDERATIONS	14
	8.1	Study Design/Endpoints	14
	8.2	Sample Size/Accrual Rate	15
	8.3	Stratification Factors	15
	8.4	Statistical Methods of Analysis	15
	8.5	Interim Disease Progression Monitoring	16
9.	ADVI	ERSE EVENTS AND REPORTING	17
	9.1	Definition of Adverse Event	17
	9.2	Radiation Related Adverse Event	17
	9.3	Chemotherapy Related Adverse Event	18

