1.2. Secondary Objectives

- 1.2.1 To quantify the extent of radiation dose sparing to the NPC containing regions that is possible without compromising tumor coverage in patients with newly diagnosed GBM
- 1.2.2 To examine the relationship between radiation dose to the NPC-containing niches and the proximity of the planning tumor volume to the NPC-containing regions.
- 1.2.3 To assess feasibility of evaluating cognitive function prospectively in patients undergoing NPC sparing RT for newly diagnosed GBM.
- 1.2.3 To explore if the potential change from baseline to six months in neurocognitive function as measured by the Mini Mental State Exam, Trail Making Test, Controlled Oral Word Association test (COWAT), Hopkins Verbal Learning Test-Revised, Digit Symbol Substitution Test is related to radiation dose to the NPC containing regions in patients treated with NPC sparing radiation for newly diagnosed GBM.

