2. BACKGROUND

2.1 Study Disease and Rationale

The current standard of care in treatment of newly diagnosed GBM is based on the European Organization for Research and Treatment of Cancer and the National Cancer Institute of Canada Clinical Trials Group (EORTC/NCIC) phase III clinical trial (1). This study randomized patients to surgical resection followed by radiation therapy plus or minus concurrent and adjuvant temozolomide and demonstrated an improvement in median survival from 12.1 months with standard radiation therapy to 14.6 months with the addition of temozolomide. This marked a significant improvement in 2 year overall survival from 10% to 27% with an improvement in five year overall survival from 1.9% to 9.8% (2), representing the first report of long term survivals of GBM.

As long term survival from GBM improves, minimizing long term toxicities of therapy becomes increasingly important. Animal studies have shown that new neurons and glia are produced throughout adult life from neural stem cell precursors in the subventricular zone of the lateral ventricles and the subgranular zone of the hippocampal dentate gyrus (3-5). These cells play an important role in injury repair within the central nervous

system (6,7). Similarly, these cells migrate to the site of inflammation caused by irradiation or brain injury (7).

Multiple animal studies have shown that neural progenitor cells are extremely sensitive to radiation (8-11). Tada et al. showed that 2 Gy of radiation effectively killed proliferating cells in both the SVZ of the lateral ventricles (8) and the subgranular zone of the dentate gyrus (9). The anti-proliferative effects last for up to 15 months after a single radiation treatment (12) and are dose dependent (8,9).

There is an association between radiation-induced neural progenitor cell impairment and neurocognitive decline after central nervous system irradiation in rodents. Cranial irradiation significantly decreases hippocampal neurogenesis and is associated with impaired performance of hippocampal-dependent tasks (13-16), indicating that newly born cells may be essential for normal hippocampal functioning.

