8.4 Statistical Methods of Analysis

All analysis will be based on the Intend-To-Treat (ITT) principle. Per-protocol will be allowed after ITT analyses.

The proportion of patients with LR in the avoidance region of the NPC will be estimated along with the exact 95% confidence interval. The lower bound 95% confidence interval of exact binomial distribution will be used to determine the acceptance of the LR rate of 25%.

All patients will count towards assessment of all objectives. However, if no patient relapses in the spared NPC containing region, we recognize that the present study will not definitively demonstrate that sparing of the NPC regions does not impact the pattern of recurrence since this is a pilot study and 2 patients received mebendazole following completion of radiation therapy but prior to relapse. Given that no intervention to date including systemic agents, radiation dose escalation, and hypofractionation has ever impacted the site of recurrence we feel it is exceedingly unlikely that mebendazole would impact our primary endpoint. However, we will evaluate if the analysis of the primary endpoint would yield different results with or without inclusion of these patients. If there is a difference both analyses will be presented in the manuscript. Even if there is no statistically significant difference

between the groups we will clearly state in our publications that 2 patients received mebendazole with their adjuvant temozolomide following completion of radiation therapy but prior to relapse.

To quantify the extent of radiation dose sparing to the NPC containing regions that is possible, patients will be binned into 4 groups according to the volume of NPC region that receives a certain dose as follows: 1) $V_{5Gy} \le 50\%$; 2) $V_{5Gy} \le 20\%$; 3) $V_{10Gy} \le 20\%$; 4) Doses higher than levels 1-3. The proportion of overall patients who meet at least the dose constraint will be estimated using a binomial distribution along with 95% confidence intervals, as well as the individual group.

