To assess the feasibility of evaluating cognitive function prospectively in this patient population, we will evaluate the six month post radiation therapy protocol compliance in terms of neuropsychological evaluations. The proportion of patients completing the planned neurocognitive assessments at both baseline and 6 months post radiation therapy will be calculated, along with the 95% confidence interval. If \geq 40% of patients did not complete at least 1 of these planned assessments, the testing will be considered not feasible.

The change in neurocognitive function from baseline to 6 months post radiation therapy will be explored by using the 5 instruments measuring neurocognitive function. The change will be summarized graphically (using, for example, boxplots) and using mean, median or score shifting etc. This will be done for each instrument separately. Correlation coefficients will be calculated to explore potential correlation between the change in neurocognitive function from the baseline and the radiation dose to the NPC-containing region.

Spearman's rank correlation coefficient will be calculated to explore an association between the closest distance (either X-, Y-, or Z-) of the planning tumor volume to the spared NPC-containing niche and the mean, minimum, and maximum radiation dose to this region.

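### By default the 40% feasibility rule scores a death before the 6-month post-radiation test as non-compliance with testing, so mortality can drive the verdict on neurocognitive testing

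*Combined protocol and SAP*

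**What the plan says.** The rule serves the secondary objective in section 1.2: "To assess feasibility of evaluating cognitive function prospectively in patients undergoing NPC sparing RT for newly diagnosed GBM". Section 8.4 presents it as an evaluation of compliance with the neuropsychological tests six months after radiation. The measure is "The proportion of patients completing the planned neurocognitive assessments at both baseline and 6 months post radiation therapy will be calculated", with a 95% confidence interval. The decision rule follows: if at least 40% "of patients did not complete at least 1 of these planned assessments, the testing will be considered not feasible".

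Two sentences earlier in section 8.4 bear on the denominator: "All analysis will be based on the Intend-To-Treat (ITT) principle", with per-protocol analysis allowed afterwards, and "All patients will count towards assessment of all objectives". The schema gives "Required sample size: 30 patients".

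Death is not mentioned in the feasibility rule. Neither the follow-up provisions (5.3), the removal criteria (5.4) nor the study calendar (6) takes patients who have died out of the denominator or asks for them to be reported separately. The plan gives no expected mortality and no expected completion rate behind the 40%.

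**The concern.** A rule framed as compliance should respond to whether patients who can be tested are tested. Here a patient who died before the visit is indistinguishable from a survivor who skipped it. In glioblastoma, deaths in the first seven or eight months are not a negligible fraction, so they take up a large part of the 40% allowance before any compliance problem arises.

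This is the only decision rule for the feasibility objective. Section 2.1 names a randomized trial of neurocognitive outcomes as the intended next step. A not-feasible label produced mainly by deaths would misinform its design, and one pooled proportion would not show whether survival or testing was the limit.

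**Working it through.** **Inputs from the documents.** Sample size 30 (schema). Threshold 40% (8.4). Median survival with temozolomide: "improvement in median survival from 12.1 months with standard radiation therapy to 14.6 months with the addition of temozolomide", and 27% alive at 2 years (both 2.1). Radiation is 60 Gy at 2 Gy per fraction, five days a week (5.2.1): 60/2 = 30 fractions, or 6 weeks. Six months after radiation is therefore about 7.4-7.5 months from its start.

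**Assumptions.** The cohort survives like the cited temozolomide arm, with survival counted from about the start of radiation. The completion rate among survivors, c, is not in the documents; values from 50% to 100% are shown.

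**Cut-off.** The plan gives no derivation to reproduce. 0.40 × 30 = 12 non-completers.

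**Survival at the visit.** Four curves:
- Exponential: S(t) = 0.5^(t/14.6). It uses the median only and implies 32% at 2 years, against 27% stated.
- Weibull: S(t) = exp(−ln 2 · (t/14.6)^k), k = ln[ln(1/0.27)/ln 2]/ln(24/14.6) = 1.28.
- Log-logistic: S(t) = 1/(1 + (t/14.6)^b), b = ln(0.73/0.27)/ln(24/14.6) = 2.00.
- Log-normal: S(t) = 1 − Φ(ln(t/14.6)/σ), σ = ln(24/14.6)/z(0.73) = 0.81.

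The last three pass through both the median and the 2-year figure.

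**Probability of a not-feasible verdict.** P(X ≥ 12), where X is binomial with n = 30 and probability 1 − S·c. Each range runs from 7.4 to 7.5 months.

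| Curve | Dead by visit | Expected deaths of 30 | c = 100% | c = 90% | c = 85% |
|---|---|---|---|---|---|
| Exponential | 29.6-30.0% | 8.9-9.0 | 0.148-0.158 | 0.418-0.432 | 0.577-0.589 |
| Weibull | 25.2-25.6% | 7.6-7.7 | 0.054-0.059 | 0.251-0.264 | 0.408-0.422 |
| Log-logistic | 20.4-20.9% | 6.1-6.3 | 0.011-0.013 | 0.115-0.125 | 0.239-0.253 |
| Log-normal | 20.1-20.6% | 6.0-6.2 | 0.010-0.012 | 0.108-0.119 | 0.229-0.244 |

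**Share of the allowance.** 6.0/12 = 50% to 9.0/12 = 75%. Expected non-completion reaches 40% when c = 0.60/S, that is 0.60/0.80 = 75% with 20% deaths and 0.60/0.70 = 86% with 30% deaths.

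**Example.** With 8 deaths, 22 patients survive. If 4 of them miss a test, 18/22 = 82% of survivors are tested, yet (8 + 4)/30 = 40% and the verdict is not feasible.

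**Alternative timing.** Section 8.1.3.3 times the visit six months from baseline. Taking baseline as the start of radiation, t = 6 gives deaths of 24.8% (exponential), 19.9% (Weibull), 14.4% (log-logistic) and 13.6% (log-normal). At c = 85%, P is 0.39, 0.22, 0.09 and 0.08.

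**Same 40% rule on survivors only.** For 21 or 22 survivors the cut-off is 9; for 23 or 24 it is 10. Across 21-24 survivors, P(not feasible) is 0.001-0.003 at c = 85%, 0.12-0.19 at 70%, 0.44-0.55 at 60% and 0.80-0.86 at 50%. The rule still detects poor compliance.

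**The case against.** **The plan does not say that deaths are failures.** Correct. The sentence "All patients will count towards assessment of all objectives" opens the paragraph about two patients who received mebendazole, so in context it is mainly about keeping them in. A reader might infer that the plan expressly counts deaths as non-compliance; the text does not support that. What remains is the intention-to-treat sentence, the requirement for tests at both times and the absence of any exclusion. Together these make it the default. Per-protocol analysis comes only afterwards and is not defined for this endpoint.

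**The threshold phrase can be read another way.** If failing to complete at least one assessment means completing neither, a patient tested at baseline who later died is not a failure and the point falls. That reading is strained: the preceding sentence requires completion at both times, and baseline testing precedes radiation, so the rule would almost never trigger. The ambiguity itself needs removing.

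**The size depends on the curve.** This stands. Section 2.1 also reports 9.8% alive at five years. The fitted curves imply 5.8% (exponential), 1.5% (Weibull), 5.6% (log-logistic) and 4.1% (log-normal). The last two match the 2-year figure that the exponential misses and come closer to the five-year figure than the Weibull, and they give the lower mortality. Quoting only 25-30% deaths would lean high.

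**Attrition by death is part of feasibility.** Also fair: the yield of paired data from enrolled patients matters for a later trial. That is a reason to report the all-enrolled proportion, not to fold it into a compliance threshold. Moving the threshold to survivors has its own weakness: the rule would usually pass with only 70% of survivors tested, and the 40% remains unjustified.

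**The consequence is limited.** The plan attaches no action to the label, section 2.1 ties the next trial to local recurrence, and the proportion and its interval are reported in any case.

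**Conclusion.** The point holds as a default reading. Intention-to-treat analysis with no provision for death makes deaths before the 6-month post-radiation test count as non-completion. On the protocol's own survival figures that is about 20-30% of patients, or half to three-quarters of the 12 non-completions that trigger the verdict. The chance of a not-feasible verdict is about 0.23-0.59 if 85% of survivors are tested, 0.11-0.43 at 90% and 0.01-0.16 at 100%. With the visit six months from baseline, the 85% figure is about 0.08-0.39.

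These figures rest on the cohort resembling the cited arm, on survival counted from about the start of radiation, on the assumed completion rates, and on reading the threshold as failure to complete both assessments.

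A reader might go further and infer that the rule largely measures survival, or is bound to give the wrong answer. The documents do not support that: under the lower-mortality curves deaths use only about half of the allowance, and with full testing of survivors the rule seldom fails. This is a low-cost improvement to a secondary objective; the primary endpoint is untouched.

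**What to change.** In section 8.4:
- Apply the 40% compliance threshold to patients alive at the 6-month visit, and state explicitly how deaths are handled.
- Reword the criterion as the proportion who did not complete both assessments.
- Report the all-enrolled proportion with its 95% confidence interval beside it, as the measure of usable paired data.
- Tabulate deaths, withdrawals and missed tests separately.
- Reconcile the 6-month time point between section 8.1.3.3 (from baseline) and section 8.4 (after radiation).

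The cost is wording only, with no new data collection. The downsides are a denominator of about 21-24 instead of 30, a slightly wider interval, and a verdict conditional on survival, which is why the all-enrolled figure should stay beside it.

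### Cognitive change is correlated with niche dose without adjustment although tumor geometry drives that dose; adjusted versions should be shown beside the raw coefficient as sensitivity analyses

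*Combined protocol and SAP*

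**What the plan says.** The objective is the second of the two items numbered 1.2.3 in Section 1.2, which begins "To explore if the potential change from baseline to six months in neurocognitive function". Section 8.4 gives the analysis: "The change in neurocognitive function from baseline to 6 months post radiation therapy will be explored by using the 5 instruments", with each instrument summarized separately, and then "Correlation coefficients will be calculated to explore potential correlation between the change in neurocognitive function from the baseline and the radiation dose" (that is, niche dose). The type of coefficient is not stated. No covariate, partial correlation or regression model is named here or elsewhere. Baseline score enters only through the change score. The one score adjustment described is age and education norming of the word-association test (Section 2.3).

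Three other places bear on this:

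- Objective 1.2.2 is "To examine the relationship between radiation dose to the NPC-containing niches and the proximity of the planning tumor volume to the NPC-containing regions".
- Section 5.2.4 defines the spared niche as the part more than 2 cm from the PTV. Its dose constraint is tightened until tumor coverage or another organ at risk would suffer.
- Section 8.1.3.2 records the X, Y and Z distances from the PTV to the spared niche and the spared-niche volume. PTV and GTV volume are not listed.

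In Section 8.4, proximity is used only in a separate analysis: "Spearman's rank correlation coefficient will be calculated to explore an association between the closest distance" and dose. The trial has one arm and no stratification (Sections 8.1.1 and 8.3).

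**The concern.** Niche dose in this trial is a by-product of tumor geometry, because the planner reduces it only as far as the tumor allows. If tumor position also affects how cognition moves over six months, a raw correlation of change with dose absorbs that effect. It can show a dose relation where there is none, or conceal a real one. There is no comparison arm to balance tumor features.

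Baseline score is a second route. A tumor that yields a higher niche dose may also lower the baseline score. Whether that biases the change score, and in which direction, depends on what happens to the deficit afterwards.

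At stake is the reading of one exploratory secondary objective. It is the only evidence in this study on dose and cognition.

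**Working it through.** **Inputs from the documents.** The sample is "Required sample size: 30 patients". Section 8.4 says that if 40% or more "did not complete at least 1 of these planned assessments, the testing will be considered not feasible". I read this as missing either the baseline or the 6-month assessment. Then 18 pairs (12/30 = 40% missing) fail and 19 (11/30 = 36.7%) pass, so there are 19 to 30 pairs if testing is feasible. The plan states no alpha, power or effect size for this correlation, so there is no figure to reproduce.

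**Assumed inputs.** Every correlation below is an assumption.

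**1. Precision.** The 95% limits around r = 0 are ±tanh(1.96/√(n − 3)): ±0.36 at n = 30 and ±0.45 at n = 19. The r detectable with 80% power is 0.49 and 0.60.

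**2. Tumor location, no dose effect.** Let a = corr(dose, location) and b = corr(change, location). The spurious correlation is a × b.

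| a | b = -0.3 | b = -0.5 | b = -0.7 |
|---|---|---|---|
| 0.4 | -0.12 | -0.20 | -0.28 |
| 0.6 | -0.18 | -0.30 | -0.42 |
| 0.8 | -0.24 | -0.40 | -0.56 |

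**3. Tumor location, true partial r = -0.3.** The marginal r is -0.3 × √((1 − a²)(1 − b²)) + a × b.

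- a = 0.6, b = +0.3: -0.3 × √(0.64 × 0.91) + 0.18 = -0.05. The relation is hidden.
- a = 0.6, b = -0.5: -0.3 × √(0.64 × 0.75) − 0.30 = -0.51. The relation is inflated.

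**4. Baseline, no dose effect.** Let ρ = corr(baseline, dose) and r = retest correlation, with equal variances.

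- *Fading deficit* (6-month score = r × baseline + error). The raw corr(change, dose) is -ρ√((1 − r)/2), and the baseline-adjusted value is 0.
- *Stable deficit* (both scores are the same true level plus independent error, and the true level is linked to dose). The raw corr(change, dose) is 0, and the baseline-adjusted partial correlation is ρ√((1 − r)/(1 + r))/√(1 − ρ²).

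| ρ | r | Fading: raw | Fading: adjusted | Stable: raw | Stable: adjusted |
|---|---|---|---|---|---|
| -0.3 | 0.5 | +0.15 | 0 | 0 | -0.18 |
| -0.3 | 0.7 | +0.12 | 0 | 0 | -0.13 |
| -0.5 | 0.5 | +0.25 | 0 | 0 | -0.33 |
| -0.5 | 0.7 | +0.19 | 0 | 0 | -0.24 |

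With r up to 0.9, the fading-deficit bias falls to as little as +0.07. If ρ = 0, both biases vanish. Signs are for scales where higher is better; Trail Making runs the other way, so they reverse there.

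**5. Nominal 5% tests with no dose effect** (simulation, 4,000 runs per scenario, r = 0.7, a = 0.6, fading-deficit model; n = 18 is one below the floor of 19).

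| Scenario | n | Raw | Given baseline and location |
|---|---|---|---|
| Location moves change by -0.4 baseline SD per SD | 30 | 32% | 5% |
| Same | 18 | 19% | 5% |
| Location lowers baseline only (correlation -0.5) | 30 | 10% | 5% |
| Same | 18 | 8% | 5% |

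The adjusted column conditions on location itself. The recorded distance is a proxy and would remove less.

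**6. Cost of adjusting.** With two covariates the limits become ±tanh(1.96/√(n − 5)): ±0.37 at n = 30 and ±0.48 at n = 19. Collinearity may cost more. The share of dose variance left after adjusting for a covariate correlated a with dose is 1 − a², which is 0.84 at a = 0.4 and 0.36 at a = 0.8.

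**The case against.** The strongest objection is that the change score is a defensible choice and baseline adjustment is not a neutral repair. With an exposure that was not randomized, the two analyses answer different questions when baseline differs with exposure. Step 4 bears this out: under a stable deficit, adjustment creates an apparent harm of dose as large as or larger than the artifact it removes under a fading one. Nothing in the documents says which model holds. This stands, so a reader who infers that regression to the mean necessarily biases the planned coefficient, or that the adjusted coefficient is the right one, goes further than the documents allow.

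The plan also limits its own claims. Both the objective and Section 8.4 speak of exploring a relation, Section 8.4 calls the trial a pilot, and no test or threshold is attached. The baseline bias, at most 0.25 in size when the deficit fades, lies inside the sampling limits. The larger location figures rest on assumed effects. This lowers the stakes, but it does not make the raw coefficient interpretable as a dose relation.

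The recorded geometry is imperfect. Tumor volume is not listed, so adjustment for tumor size cannot be promised from the listed data. The distance runs to the spared niche, which lies more than 2 cm from the PTV by definition, so it is truncated. Where it does vary, it may track dose closely. These points also stand, and they limit what the distance-adjusted version can show.

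**Conclusion.** The point holds as a minor one. The planned correlation is unadjusted while the protocol makes niche dose depend on tumor geometry, so location can create or hide a dose relation. Baseline differences linked to dose can bias the raw or the baseline-adjusted coefficient, depending on whether the deficit is stable or fades.

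The assumed inputs put the location artifact at -0.12 to -0.56. The baseline artifact is +0.07 to +0.25 in the raw coefficient if the deficit fades, and -0.13 to -0.33 in the adjusted one if it is stable. None of these inputs comes from the documents.

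A reader might infer that a spurious coefficient would launch or shape the later randomized trial. Section 2.1 makes that trial conditional on local recurrence in the spared region, and no decision is tied to this correlation. The primary endpoint is not touched.

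**What to change.** In Section 8.4, keep the raw change-dose correlation and add two coefficients beside it for each instrument:

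- (a) a partial Spearman correlation of the 6-month score with dose, adjusted for baseline score (or a rank regression of the 6-month score on dose and baseline);
- (b) the same, also adjusted for the recorded distance from the PTV to the spared niche.

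Give each a 95% confidence interval and the number of pairs. Name the coefficient type for the raw version too; Spearman would make the three comparable. State that all are exploratory sensitivity analyses, that none is taken as the correct one, and that a dose signal is called robust only if it is consistent across versions. Note the 2 cm floor and report the correlation of distance with dose, so that the reader can see how much dose variation remains in (b).

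The cost is a few lines of analysis and one or two degrees of freedom with 19 to 30 pairs if testing is feasible. Version (b) may be imprecise, and the report should say so. No new data are needed. Adjusting for tumor size as well would require adding PTV or GTV volume to the recorded items.

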5.2 Radiation

5.2.1 Radiation Simulation and Prescription

Patients will be treated to a total dose of 60 Gy with a once daily fractionation schedule of 2 Gy per fraction, administered five days per week. All patients will undergo CT simulation with intravenous contrast. In addition they will undergo MRI simulation with both T1 with gadolinium as well as FLAIR sequences. They will be treated in a supine position using an aquaplast mask system for immobilization. CT image data will be reconstructed in approximately 3 mm slice thickness and manually coregistered with T1 post-gadolinium and FLAIR sequence MRI.

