5.2.4 Neural Progenitor Cell Containing Niches

The NPC containing niches will be defined as a 5 millimeter region adjacent to the lateral wall of the lateral ventricle and the entire hippocampus. These areas will be contoured on the simulation CT scan using a manually coregistered MRI as a reference. A portion of the NPC-containing niches which is >2 cm from the PTV will be contoured as a region of interest and labeled as "NPC_for_sparing". A radiation treatment plan will be generated in which we attempt to limit the RT dose to the "NPC_for_sparing" region as much as possible without compromising the radiation dose coverage of the tumor. Specifically, using inverse planning, the dose constraint and weight of the "NPC_for_sparing" region will be progressively tightened until additional iterations would to result in compromised tumor coverage or unacceptable dose to another organ at risk. The extent of NPC sparing that is possible will be recorded for each patient in terms of the volume of the "NPC_for_sparing" region, and the mean, minimum, and maximum dose to this area.

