8.1.3 Secondary Endpoints

- 8.1.3.1 The extent of NPC-sparing will be recorded for each patient. Patients will be binned into 4 groups according to the volume of NPC region that receives a certain dose as follows: 1) V_{5Gy}≤50%; 2) V_{5Gy}≤20%; 3) V_{10Gy}≤20%; 4) Doses higher than levels 1-3.
- 8.1.3.2 The X-, Y-, and Z- coordinate distances in centimeters will be recorded from the most proximal point of the planning tumor volume to the closest point of the spared NPC-containing niche. The mean, minimum, and maximum radiation dose to the spared NPC-containing region will be recorded for each patient. In addition, the volume of the "NPC_for_sparing" region will be recorded.
- 8.1.3.3 Completion of neurocognitive testing and Neurocognitive function will be assessed at baseline, and at six, twelve, and twenty-four months from baseline using the Mini Mental State Exam, Trail Making Test A & B, Controlled Oral Word Association Test, Hopkins Verbal Learning Test-Revised and the Digit Symbol Substitution Test.

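### For objective 1.2.2, section 8.4 correlates spared-region dose with a single-axis offset, most naturally the smallest, although 8.1.3.2 records all three components needed for the 3-D distance

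*Combined protocol and SAP*

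**What the plan says.** Secondary objective 1.2.2 is worded as follows: "To examine the relationship between radiation dose to the NPC-containing niches and the proximity of the planning tumor volume to the NPC-containing regions". It names no axis and is not confined to the spared part of the niches.

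For the data, section 8.1.3.2 states: "The X-, Y-, and Z- coordinate distances in centimeters will be recorded". They run "from the most proximal point of the planning tumor volume to the closest point of the spared NPC-containing niche". All three components are therefore captured, and the wording reads as one pair of points.

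For the analysis, section 8.4 takes Spearman's coefficient between "the closest distance (either X-, Y-, or Z-) of the planning tumor volume to the spared NPC-containing niche" and the mean, minimum and maximum dose to that region. Nothing in the protocol combines the three components, and no further rule is given for choosing among them. The analysis is labelled exploratory, with no alpha, power or target correlation.

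Section 5.2.4 fixes the geometry of the spared structure: "A portion of the NPC-containing niches which is >2 cm from the PTV will be contoured as a region of interest".

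**The concern.** Objective 1.2.2 is about how near the tumour volume is to the niches. A displacement in space has three components, and one of them alone does not say how long it is. If the smallest is used, a patient whose tumour lies far from the niche almost straight along one axis is scored as very close. The axis that supplies the value can also differ from patient to patient, so the variable does not measure the same thing in everyone.

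Spearman uses only ranks, so misordering patients acts directly on the planned statistic. This is the only analysis in 8.4 that relates dose to proximity. If it is run as written, a real relation could be reported as weak or absent because of how distance was coded.

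**Working it through.** The plan states no figure for this analysis, so there is nothing to reproduce. The check has a part that needs no assumptions and a part that is only illustrative.

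**Inputs from the protocol.** Offsets X, Y and Z in cm (8.1.3.2); a single-axis value correlated with dose by Spearman (8.4); a spared structure more than 2 cm from the planning tumour volume (PTV) (5.2.4); CT slices of about 3 mm (5.2.1); 30 patients (schema and 8.2.1).

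**1. Bound, no assumptions.** With D = sqrt(dX² + dY² + dZ²) and m the smallest absolute offset, D² ≥ 3m², so 0 ≤ m ≤ D/sqrt(3) = D/1.73.
- At D = 4 cm, m can be anywhere from 0 to 4/1.73 = 2.31 cm.
- m is below 2 cm for every patient with D below 2 × 1.73 = 3.46 cm. The smallest offset therefore cannot be the distance that 5.2.4 uses for its 2 cm rule.

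**2. Rank reversal, no assumptions.**

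| Offsets (cm) | 3-D distance | Smallest offset |
|---|---|---|
| 0, 0, 5 | sqrt(25) = 5.00 | 0 |
| 1.5, 1.5, 1.5 | sqrt(3 × 2.25) = 2.60 | 1.5 |

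Both satisfy the 2 cm rule, and the two measures order them oppositely.

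**3. Size, illustrative.** Assumptions, none from the documents: direction uniform on the sphere; PTV-to-niche distance d uniform on 0-3, 0-6 or 2-5 cm; distance to the spared structure D = max(d, 2); 400,000 draws each.

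| Quantity | 0-3 cm | 0-6 cm | 2-5 cm |
|---|---|---|---|
| Spearman, smallest offset with D | 0.14 | 0.41 | 0.29 |
| Spearman, smallest offset with d | 0.11 | 0.40 | 0.29 |
| Spearman, D with d | 0.84 | 0.98 | 1.00 |
| Share tied at D = 2 cm | 2/3 = 67% | 2/6 = 33% | 0% |

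Among pairs of patients whose D differs by at least 1 cm, the smallest offset orders 29% (0-6 cm) and 34% (2-5 cm) the wrong way. Under 0-3 cm there are no such pairs, because D spans only 2 to 3 cm.

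**4. What the 2 cm rule does to the 3-D distance.** Any niche that crosses the 2 cm boundary has its nearest spared point at about 2 cm, within the slice resolution. Those patients are tied or nearly tied on D. The last two rows of the table show the effect: under 0-3 cm, two thirds are tied and D tracks the distance to the whole niche at 0.84. The protocol does not give the real share.

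**5. Sensitivity to dose fall-off.** Step 3 compares offsets with D, whereas 8.4 correlates distance with dose. Suppose instead that dose falls twice as fast along one axis (again an assumption), so that the distance relevant to dose is sqrt((2dX)² + dY² + dZ²). Spearman with that distance is:

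| Measure | 0-3 cm | 0-6 cm | 2-5 cm |
|---|---|---|---|
| 3-D distance D | 0.42 | 0.87 | 0.75 |
| The steep axis, named in advance | 0.95 | 0.81 | 0.86 |
| Smallest offset | 0.18 | 0.41 | 0.29 |

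The 3-D distance is not always the best covariate. The smallest offset is the weaker of the two against it in all three cases.

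**The case against.** The strongest reply is that agreement with D is a yardstick the protocol never set. The planned correlation is with dose, and D is the ideal covariate only if dose falls off equally in every direction, which the documents do not say. This stands. Step 5 shows that a well-chosen fixed axis can do better than D, so a reader who infers that any single axis loses severely goes further than the documents allow. What survives is narrower: the smallest offset is poor under both fall-off patterns, and 8.4 names no axis in advance.

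A second reply is that the wording is merely loose and a direction-free distance was meant, since 5.2.4 already uses one. That is plausible, but the parenthesis in 8.4 then says something else and should be corrected. A reader might also suppose that the largest offset is intended, which would track D much better. Nothing in the text supports that; the word used is closest.

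Third, the 3-D distance to the spared structure may itself be uninformative for many patients because of the 2 cm rule. This is right, and it is why the fix does not stop there.

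Finally, the analysis is exploratory and drives no decision, and because all components are recorded, nothing is lost irreversibly. Both statements are correct, and they set the severity.

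**Conclusion.** The point holds, as a minor one. On its natural reading, section 8.4 uses a variable that does not measure proximity and can reverse patient ranks, although the components of a proper distance are already collected. The bound and the rank reversal need no assumptions. The correlations of 0.14, 0.41 and 0.29 rest on assumed random directions and assumed distance ranges. They should not be read as the expected loss in this trial, because how well any distance tracks dose depends on a fall-off that the documents do not give.

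Nor do the documents support the inference that objective 1.2.2 cannot be answered: the recorded data allow the better analysis at any time. The primary endpoint, the sample size of 30 and the stopping rule are unaffected.

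**What to change.** In 8.4, replace the single-axis wording with the shortest 3-D distance, sqrt(dX² + dY² + dZ²), computed from the offsets recorded under 8.1.3.2. Keep Spearman and the mean, minimum and maximum spared-region dose. Single-axis correlations may be shown descriptively, provided all three axes are reported.

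Report how many patients lie at the 2 cm boundary. Because objective 1.2.2 concerns "the proximity of the planning tumor volume to the NPC-containing regions", add the shortest 3-D distance from the PTV to the whole contoured niche (zero if they overlap), correlated with mean dose to the whole niche.

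The first change is wording only. The whole-niche analysis needs one extra distance and dose export per patient, from contours already drawn under 5.2.4. Treatment planning does not change.
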